C _{max}	maximum serum concentration
C _{min}	minimum serum concentration
CTCAE	common terminology criteria for adverse events
ECG	electrocardiogram
EFS	event free survival
EOT	end of treatment
LLOQ	lower limit of quantitation
MedDRA	Medical Dictionary for Regulatory Activities
MRI	magnetic resonance imaging
NCI	National Cancer Institute
PK	pharmacokinetic
QTcF	corrected QT interval by Fredericia
RA	retinoic acid
SAE	serious adverse event
SD	standard deviation
TEAE	treatment emergent adverse event
t _{max}	Time to maximum serum concentration
t _{1/2}	half-life

1. INTRODUCTION

The purpose of this statistical analysis plan (SAP) is to describe the procedures and the statistical methods that will be used to analyze and report results for BGB-dinutuximab beta-101. The focus of this SAP is for the final analysis specified in the study protocol.

2. STUDY OVERVIEW

This is an open-label, multi-center, single-arm, Phase 1 study evaluating the safety and pharmacokinetics of dinutuximab beta as maintenance therapy in Chinese patients with high-risk neuroblastoma.

[figure not shown]
Potential patients will be screened for eligibility before study enrollment (screening period ≤ 28 days). The study will recruit approximately 8 patients who will be hospitalized (with a full resuscitation equipment) on Day 1 of each cycle and will receive continuous infusion of dinutuximab beta administered at a dose of $10 \text{ mg/m}^2/\text{day}$ for 10 consecutive days in 35-day cycles (total dose $100 \text{ mg/m}^2/\text{cycle}$). Patients must be administered in a unit with a full resuscitation equipment. Patients will be discharged from the hospital at the investigator's discretion. Patients will continue to receive 13-cis-RA $160 \text{ mg/m}^2/\text{day}$, divided approximately into 2 equal doses and given orally twice a day for 14 days after completion of dinutuximab beta infusion.

Patients may receive up to five 35-day cycles in the absence of relapse, disease progression or unacceptable toxicity.

Refer to [Figure 1](#) for an overview of the study design and Appendix 1 for details on study assessments and procedures that will be carried out during the study.

The maximum duration of participation (Screening Visit to Safety Follow-up Visit) for individual patients will be approximately 35 weeks. Each patient will participate in the screening period (≤ 28 days), study intervention infusion period (≤ 25 weeks), and a post-infusion period (≤ 6 weeks). Additional clinical follow-up might be needed depending on findings during the study.

Figure 1: Study Schema

Abbreviations: EOT, end of treatment; PK, pharmacokinetic(s).

All patients will be closely monitored for AEs throughout the study and for 40 days after the last dose of study drug.

PK analysis will be performed for dinutuximab beta.

Tumor assessments or monitoring will be performed by the investigators at Screening Visit, end of treatment Cycle 3, and end of treatment Visit per their clinical practice. International Neuroblastoma Response Criteria (INRC) (Brodeur et al 1993) is recommended as a reference for response evaluation in patients evaluable for tumor assessment. Patients who, at the time of progression, have an ongoing AE that leads to treatment discontinuation and who have completed the scheduled Safety Follow-up Visit will be followed up until the event resolves, the investigator assesses the event as stable, the patient is lost to follow-up, or the patient starts a new anticancer therapy, end of study, whichever comes first.

Patients who have discontinued study drug(s) will return to the site for an End-of-Treatment (EOT) Visit. After the EOT Visit, patients will have scheduled follow-up visits for safety.

3. STUDY OBJECTIVES

3.1. Primary Objective

- To assess the safety and tolerability of ≤ 5 treatment cycles of dinutuximab beta in combination with 13-cis-retinoic acid (RA) as maintenance therapy in Chinese patients with high-risk neuroblastoma.
- To characterize the pharmacokinetics (PK) of dinutuximab beta in Chinese patients.

3.2. Secondary Objective

There is no secondary endpoint.

3.3. Exploratory Objective

- To explore the preliminary anti-tumor activity and event free survival rate (EFS), of ≤ 5 treatment cycles of dinutuximab beta in combination with 13-cis-RA as maintenance therapy in Chinese patients with high risk neuroblastoma, if applicable

4. STUDY ENDPOINTS

4.1. Primary Endpoint(s)

- Adverse events (AEs) characterized by type, frequency, severity (as graded by the National Cancer Institute-Common Terminology Criteria for Adverse Events [NCI-CTCAE] version 5.0), timing, seriousness, and relationship to study drug(s); and other safety assessments.
- PK parameters of dinutuximab beta, including but not limited to area under the concentration-time curve (AUC), maximum serum concentration (C_{max}), minimum serum concentration (C_{min}), time to C_{max} (t_{max}), and half-life ($t_{1/2}$), if data permits.

4.2. Secondary Endpoints

There is no secondary endpoint.

4.3. Exploratory Endpoints

- EFS is defined as the time from initiating study drug(s) to disease progression, death from any cause, relapse, secondary malignancy as assessed by investigators, including EFS rate at 6 months as measured by Kaplan-Meier method

5. SAMPLE SIZE CONSIDERATIONS

The study plans to enroll 8 patients as recommended for PK studies by Center of Drug Evaluation (CDE) technical guidance on clinical pharmacokinetic study of chemical drugs ([CDE of National Medical Products Administration \(NMPA\) 2005](#)). Therefore, a sample size of 8 patients is proposed in this single-arm PK study.

6. STATISTICAL METHODS

6.1. Analysis Sets

The Safety Analysis Set includes all patients who received any dose of any study drug. The safety analysis set is used for all primary safety and efficacy analyses

The PK analysis set includes patients who have at least one available post-baseline PK data in Safety Analysis Set. The PK analysis set will be used for PK analyses.

6.2. Multiplicity Adjustment

Since no formal hypothesis is tested in this study, multiplicity adjustment is not needed.

6.3. Data Analysis General Considerations

6.3.1. Definitions and Computations

Study drugs include dinutuximab beta and 13-cis-RA therapy.

Study day will be calculated in reference to the date of the first dose of study drug. For assessments conducted on or after the first dose, the study day will be calculated as assessment date – the first dose date + 1). For assessments conducted before the first dose, study day is calculated as (assessment date – the first dose date). There is no study day 0. In the situation where the event date is partial or missing, the date will appear partial or missing in the listings. Study day and any corresponding durations will be presented based on the imputations specified in Appendix 1.

Unless otherwise specified, a baseline value is defined as the last non-missing value collected before the first dose of study drug.

All calculations and analyses will be conducted using SAS® Version 9.4 or higher.

6.3.2. Conventions

No formal hypothesis will be tested in this study. Data will be mainly analyzed descriptively. Confidence intervals will be constructed to describe the precision of the point estimates of interest.

Unless otherwise specified, the following conventions will be applied to all analyses:

- 1 year = 365.25 days. Number of years is calculated as (days/365.25) rounded up to 1 decimal place.
- 1 month = 30.4375 days. Number of months is calculated as (days/30.4375) rounded up to 1 decimal place.
- Duration of image-based event will be based on the actual date the radiograph was obtained rather than the associated visit date.
- For laboratory results collected as < or >, a numeric value, 0.000000001 will be subtracted or added, respectively, to the value.
- For by-visit observed data analyses, percentages will be calculated based on the number of patients with non-missing data as the denominator, unless otherwise specified.

- For continuous endpoints, summary statistics will include n, mean, standard deviation, median, Q1, Q3 and range (minimum and maximum).
- For discrete endpoints, summary statistics will include frequencies and percentages.

6.3.3. Handling of Missing Data

Missing data will not be imputed unless otherwise specified elsewhere in this SAP. Missing dates or partially missing dates will be imputed conservatively for adverse events and prior/concomitant medications/procedures. Specific rules are provided in [Appendix 2](#).

By-visit endpoints will be analyzed using observed data unless otherwise specified.

6.4. Patient Characteristics

6.4.1. Patient Disposition

The number (percentage) of patients treated, discontinued from the study, reasons for discontinued from the study, and the duration of study follow-up will be summarized in the safety analysis set. The patients who discontinued treatment and the primary reason for the end of treatment will be summarized among patients who were treated.

The following patient disposition information will be summarized separately for dinutuximab and 13-cis-RA when appropriate:

- Number of patients treated
- Number (%) of treated patients who discontinued from treatment
- Reason(s) for treatment discontinuation
- Number (%) of treated patients who discontinued from study
- Reason(s) for study discontinuation

6.4.2. Protocol Deviations

Important protocol deviation criteria will be established, and patients with important protocol deviations will be identified and documented. Important protocol deviations will be listed.

6.4.3. Demographic and Other Baseline Characteristics

Demographics and other baseline characteristics will be summarized using descriptive statistics in the safety analysis set, including the following variables:

- Age
- Sex
- Height
- Weight
- BMI

- Performance status

6.4.4. Disease History

The number (percentage) of patients reporting a history of disease and characteristics, as recorded on the eCRF, will be summarized in the safety analysis set. A listing of disease history will be provided.

6.4.5. Prior Anticancer Therapies

Prior systemic therapies, prior anti-cancer radiotherapy, and prior stem cell transplantation will be summarized in the safety analysis set. The variables include number of patients with any prior anti-cancer therapy, number of prior regimens, and best overall response for prior systemic therapies, and transplantation type, number of transplantations for prior stem cell transplantation. The therapies with the same sequence/regimen number are counted as one prior therapy.

6.4.6. Prior and Concomitant Medications

Prior medications are defined as medications that started and stopped before the first dose of study drug. Concomitant medications will be defined as medications that (1) started before the first dose of study drug and were continuing at the time of the first dose of study drug, or (2) started on or after the date of the first dose of study, before the last dose of any study medication and continue up to 40 days after the patient's last dose (as of the Safety Follow-up Visit).

Prior and concomitant medications will be coded using the version B3 202203 or higher of World Health Organization Drug Dictionary (WHO DD) drug codes. They will be further classified to the appropriate Anatomical Therapeutic Chemical (ATC) code.

The number (percentage) of patients reporting prior and concomitant medications will be summarized by ATC medication class and WHO DD preferred name in the safety analysis set. A listing of prior and concomitant medications will be provided.

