The guidelines for pain control must be followed strictly for the whole study duration. If a patient has an unacceptable pain-toxicity profile, he/she might need more intense pain treatment such as intravenous morphine after Day 5. If this is the case, in the following cycles, the treatment team should again try to taper intravenous morphine.

AEs and concomitant medications are documented throughout all phases.

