10.1.5. Prior and Concomitant Medications

Prior medications will be defined as medications that stopped before the day of first dose of study drug(s). Concomitant medications will be defined as medications that 1) started before the first dose of study drug(s) and were continuing at the time of the first dose of study drug(s), or 2) started on or after the date of the first dose of study drug(s) up to 40 days after the patient's last dose (as of the Safety Follow-up Visit). Concomitant medications will be coded using the World Health Organization Drug Dictionary drug codes and will be further coded to the appropriate Anatomical Therapeutic Chemical code indicating therapeutic classification. Prior and concomitant medications will be summarized and listed by drug and drug class. A listing of prior and concomitant medications will be provided.

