8. CHANGES IN THE PLANNED ANALYSIS

Table 3: Statistical Analysis Plan Changes

SAP version	Approval date	Change made from	Rationale of the change	Description of the change
1.0	06 July, 2023	Protocol Amendment 1.0	No or very few important protocol deviations are expected.	Remove summary of important deviations.

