- ⁿ Tumor assessments will be performed by the investigators at Screening Visit, end of treatment Cycle 3 and end of treatment Visit per their clinical practice. The INRC ([Brodeur et al 1993](#)) is recommended as a reference for response evaluation in patients evaluable for response. Tumor assessments may include MRI and/or CT scan and/or ¹²³I-MIBG scan and/or ¹⁸F-FDG-PET and/or bone marrow assessment.
- ^o Concomitant medications will be defined as medications that started before the first dose of study drug(s) and were continuing at the time of the first dose of study drug(s), or started on or after the date of the first dose of study drug(s) up to 40 days after the patient’s last dose (as of the Safety Follow-up Visit) in Section 10.1.5 of the protocol.

X: evaluations must be regularly repeated during the timepoints indicated according to routine medical care to ensure safe treatment of the patient.

Table 4: Dinutuximab Beta PK Sampling Schedule

Cycle	Cycle 1 (35 days per cycle)							Cycle 2, 3, and 4	
Time	D1 Predose	D3	D8	D11	D15 ^a	D22 ^a	D29	D1 Predose	D11
Window Allowed	-30 mins ^b	± 1 h ^c	± 1 h ^c	-5 mins ^d				-30 mins ^b	-5 mins ^d
PK Serum Sample	X	X	X	X	X	X	X	X	X

Abbreviation: PK, pharmacokinetic(s).

^a PK sampling on Day 15 and Day 22 in Cycle 1 is optional. That adjustment needs to be aligned with pharmacologists. PK sampling on Day 29 in Cycle 1 is required even if the infusion time will be delayed or extended.

^b 30 minutes before starting infusion.

^c Infusion starting time ± 1 hour.

^d 5 minutes before the end of infusion, even if the infusion time will extend to the next days.

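### SAP 6.4.6 narrows the protocol's definition of concomitant medication without declaring it: new starts from the last-dose day on are excluded, and read literally so are short courses first started on treatment

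*SAP*

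**What the plan says.** Both documents define concomitant medication in two limbs.

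- **Limb (1)** is the same in substance in both. In SAP 6.4.6 it covers drugs that "started before the first dose of study drug and were continuing at the time of the first dose of study drug".
- **Limb (2), protocol 10.1.5**, covers drugs that "started on or after the date of the first dose of study drug(s) up to 40 days after the" last dose. It sets no condition on the stop date.
- **Limb (2), SAP 6.4.6**, begins with a start on or after the first dose, then adds "before the last dose of any study medication and continue up to 40 days after the" last dose.
- **SAP Appendix 1, footnote o**, returns to the protocol rule and cites protocol 10.1.5: "or started on or after the date of the first dose of study drug(s) up to 40 days after the patient", with the sentence running on to the last dose. Neither added condition appears there.

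The other SAP category cannot take in what limb (2) leaves out: "Prior medications are defined as medications that started and stopped before the first dose of study drug". SAP Section 8 records one departure from the protocol, "Remove summary of important deviations", and says nothing about medications. On collection, protocol 7.3 states that "AEs and concomitant medications are documented throughout all phases".

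**The concern.** The SAP holds two definitions that classify the same record differently. The one in the methods section, which a programmer would follow, is the one that departs from the protocol.

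Two groups of drugs are at risk. The first is anything newly started in the 40-day follow-up. SAP 6.6.2 counts treatment-emergent adverse events through 40 days after the last dose, or until new anti-cancer therapy if that comes earlier. The report could therefore show a follow-up event without the drug newly started to treat it, although the drug was recorded. The second group is drugs first started during treatment and stopped within a cycle, such as those given for a reaction. On the literal wording these belong to no category.

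Tolerability is a primary objective, and supportive medication is part of the context in which a reader judges it.

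**Working it through.** The plan states no figure on this point, so there is none to reproduce. The check is to write each definition as a date rule and compare the results.

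**Inputs**

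- First dose: F = study day 1.
- Cycle length: 35 days, up to 5 cycles (protocol 3.1).
- Last planned study-drug day in a cycle: Day 25, for 13-cis-RA (protocol Figure 1 legend).
- Last dose for a completer without delays: L = 4 × 35 + 25 = 165.
- End of the 40-day window: L + 40 = 205.

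**Rules for limb (2)**

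- Protocol 10.1.5 and footnote o: F ≤ start ≤ L + 40.
- SAP 6.4.6, literal: F ≤ start < L and stop ≥ L + 40.
- SAP 6.4.6, middle reading (must run past the last dose): F ≤ start < L and stop > L.
- SAP 6.4.6, cap reading (40 days only bounds the window): F ≤ start < L, with no condition on stop.

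Limb (1) is applied under every rule: start < F and stop ≥ F.

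**Illustrative courses** (invented to test the rules; not trial data)

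| Start to stop (study day) | Protocol | SAP literal | SAP middle | SAP cap |
|---|---|---|---|---|
| −3 to 11 (limb 1) | yes | yes | yes | yes |
| 1 to 5 | yes | no | no | yes |
| 1 to 11 | yes | no | no | yes |
| 38 to 39 | yes | no | no | yes |
| 85 to 92 | yes | no | no | yes |
| 160 to 175 | yes | no | yes | yes |
| 160 to 205 | yes | yes | yes | yes |
| 165 to 172 | yes | no | no | no |
| 175 to 185 | yes | no | no | no |

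No course in the table meets the SAP's prior definition, so each *no* means neither prior nor concomitant.

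**What follows**

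1. The last two rows fail under all three readings of SAP 6.4.6, because the start condition is explicit. The span affected is Day 165 to Day 205, which is 205 − 165 + 1 = 41 days. That is 41/205 = 20% of the days from first dose to the end of the window.
2. The short on-treatment courses fail under the literal and middle readings and are kept under the cap reading. This part depends on the reading chosen.
3. The two rows that start on Day 1 are coded in whole days, so limb (1) cannot apply to them. If the start is recorded as before the first infusion and the drug is continuing at first dose, limb (1) captures it and both move to *yes*.
4. The planned table counts patients by drug class and preferred name. With 8 patients, one patient lost for a given name moves its percentage by 1/8 = 12.5 points. The number of courses classified *no* does not measure the effect on that table.

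**The case against.** The strongest reply is that SAP 6.4.6 is a garbled sentence and not a deliberate rule. Its 40-day phrase can be read as a cap that echoes the protocol. Other parts of the SAP support this. Appendix 2 imputes partial dates to sort each medication into prior or concomitant, with no third class. Footnote o repeats the protocol rule, and Section 8 declares no change. This stands as evidence of intent, and it means the loss of short on-treatment courses is not certain. It does not rescue drugs started on or after the last-dose day, since the start condition is unambiguous.

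A reader might also infer that the opioids, antihistamines and other planned supportive drugs would be systematically left out. The documents do not support that. Protocol 6.1 and 6.2 place antihistamine, analgesic premedication and the morphine bolus before the infusion, and start gabapentin 3 days earlier. Where such a drug is running at first dose, limb (1) captures it. Because the table counts patients and not courses, a patient counted for a drug in Cycle 1 stays counted whatever happens to later courses. What remains uncertain is how the case report form records these entries. Date-only starts on Day 1, or a bolus entered as its own record, could still miss limb (1). The documents do not settle this.

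Finally, concomitant medication sits under patient characteristics (SAP 6.4) and not under safety analyses (SAP 6.6), and the data are collected regardless. That is correct and limits the consequence.

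**Conclusion.** The inconsistency is real and should be corrected. It is certain that SAP 6.4.6 conflicts with protocol 10.1.5 and with footnote o, that the change is undeclared, and that new starts from the last-dose day on are excluded. The Day 165 to Day 205 span assumes five cycles without delay and a comparison by date.

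The exclusion of drugs first started on treatment and stopped before 40 days after the last dose holds on the literal wording only. The likely loss is therefore agents first started after the first dose, for example drugs given for reactions, if the literal reading is programmed, and all new starts in follow-up under any reading.

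The effect stops at the concomitant medication summary, and at its listing if that uses the same definition. A reader might infer that the primary safety results are distorted. They are not: no adverse event, pharmacokinetic or event-free survival derivation uses this definition.

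**What to change.** Replace limb (2) of SAP 6.4.6 with the rule in protocol 10.1.5 and footnote o: any drug whose start date falls from the first-dose date through 40 days after the last dose of any study drug, whether or not it is ongoing. If the narrower rule is intended, declare and justify it in SAP Section 8, state whether the 40-day phrase is a cap or a required duration, and correct footnote o to match.

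Either route costs little: the first is one sentence, and the second adds a Section 8 entry and a footnote correction. Neither needs extra data, because medications are already collected throughout the study.

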6.4.7. Medical History

Medical History will be coded using Medical Dictionary for Regulatory Activities (MedDRA) Version 25.1 or higher. The number (percentage) of patients reporting a history of any medical condition, as recorded on the CRF, will be summarized by system organ class and preferred term in the safety analysis set. A listing of medical history will be provided.

6.5. Efficacy Analysis

6.5.1. Efficacy Endpoint(s)

The analysis of event free survival (EFS) is based on the safety analysis set. EFS is defined as the time from initiating study drug(s) to disease progression, death from any cause, relapse, secondary malignancy as assessed by investigators. The distribution of EFS, including median, Q1 and Q3, and event-free rates at the 6th month, will be estimated using the Kaplan-Meier

method for each treatment group. Ninety-five percent CIs for median and Q1 and Q3 of EFS will be estimated using the method of Brookmeyer and Crowley ([Brookmeyer and Crowley, 1982](#)), and 95% CIs for event-free rates will be estimated using Greenwood's formula ([Greenwood, 1926](#)).

The censoring rules for the primary analysis of EFS are presented in [Table 1](#).

Table 1: Handling of Intercurrent Events and Missing Values of Event Free Survival

	Derivation rules	Outcome
No event at the time of data cut-off or withdrawal from study or lost to follow up	Date of last adequate radiologic assessment prior to or on date of data cut-off or withdrawal from study	Censored
Intercurrent events		
Discontinuation of the treatment	Tumor assessment data collected after discontinuation of study treatment will be used for analysis (treatment policy strategy)	No impact
New anticancer therapy started prior to EFS events.	Last adequate disease assessment before the new anticancer therapy (hypothetical strategy)	Censored
Missing values not related to intercurrent events		
Patients' withdrawal from the study or lost to follow-up	Last adequate disease assessment prior to patient withdrawal from the study (hypothetical strategy)	Censored
No baseline or post-baseline disease assessments without death	Date of the first dose	Censored
disease assessments with death	Date of death	Event

